5.8.2 Handling of Participant Withdrawals or Termination

Efforts will be made prior to stating that a participant is lost to follow up (LTF) by contacting the participant with the contact information provided pre-operatively either by phone/text/email. We will also obtain a friend/family member's contact information to contact the subject in order to avoid LTF.

If the IANB fails to provide adequate lip numbness after the second injection and after a wait time of a further 15 minutes (total wait time 30 minutes), the subject will discontinue with the study agent/control agent, and will be excluded from the study. Also, subjects who need supplemental injections more than 2 times will be excluded from the study. The treating dentist will be unblinded and routine protocol will be followed; Lidocaine 2% with 1:100,000 epinephrine will be administered either with an IANB, infiltration or intraosseous anesthesia as decided by the treating dentist. Every failure for these reasons will be noted by the researchers and analyzed at later time to investigate possible difference in success of each of the two LA.

The study team will try to determine reasons for discontinuation and a subject disposition document will be completed to record reason for discontinuation. Subjects who decide to discontinue participation from the study will be provided with contact information of the PI and the study team if any questions or concerns arise at a later point. If the subject would like written confirmation of their discontinuation, a withdrawal letter will be given to them, signed by the PI. It will not be required for subjects to return to the clinic for any safety follow-up visits.

5.9 Premature Termination or Suspension of Study

This study may be temporarily suspended or prematurely terminated if there is sufficient reasonable cause. Written notification, documenting the reason for study suspension or termination, will be provided by the suspending or terminating party to investigator and regulatory authorities. If the study is prematurely terminated or suspended, the PI will promptly inform the IRB and will provide the reason(s) for the termination or suspension.

Circumstances that may warrant termination or suspension include, but are not limited to:

- Data that are not sufficiently complete and/or evaluable
- Insufficient compliance to protocol requirements
- Determination of unexpected, significant, or unacceptable risk to participants
- Determination of futility
- Lack of funding

Study may resume once concerns about safety, protocol compliance and data quality are addressed and satisfy the sponsor, IRB and/or FDA.

CONFIDENTIAL

6 Study Agent and Procedural Intervention

6.1 Study Agent and Control Description

Bupivacaine HCl (1.8mL) 5% concentration, with epinephrine (1:200,000) is the investigational product. It exists in liquid form in cartridges. Bupivacaine is a FDA approved marketed anesthetic drug and meets IND Exemption.

Lidocaine HCl (1.7mL) 2% concentration with epinephrine (1:100,000) is the control agent. It exists in liquid form in cartridges. Lidocaine is a FDA approved marketed anesthetic drug.

6.1.1 Acquisition

Both the study agent and the control product exist in clinical supply (NYU Dentistry Formulary) available as standard of care and will be obtained from the clinical supply on 7th floor in the Endodontics Department (7W), purchased by the Endodontic department.

6.1.2 Formulation, Appearance, Packaging, and Labeling

Bupivacaine HCl (1.8mL) 5% concentration, with epinephrine (1:200,000) is the investigational product. Lidocaine HCl (1.7mL) 2% concentration with epinephrine (1:100,000) is the control agent. Both products exist in liquid form; available in cartons containing 5 blisters of 10X1.8 mL and 10X1.7 mL glass cartridges, respectively. Both products are commercially available. Products are available for human use in the form, route and dose planned in this trial.

6.1.3 Product Storage and Stability

Both products should to be stored at room temperature below 25°C (77°F) and should be protected from light until expiration date printed on each cartridge. One cartoon containing 5 blisters of 10X1.8 mL of Bupivacaine, in total containing 50 cartridges and one cartoon containing 5 blisters of 10X1.7 mL Lidocaine in total containing 50 cartridges will be obtained initially from the supply desk. Those initial cartoons will be stored in a locked cabinet on the 7th floor which will be only accessible by the study team. A study product log will be created. The number of used and remaining drugs will be registered in this study product log. Weekly, the remaining cartridges will be counted. New cartoons will be obtained again from the supply desk when necessary.

6.1.4 Preparation

Products are packaged for ready for use. No additional preparation is needed. However, the glass cartridges will be covered with opaque tape to mask content. Each masked cartridges with have unique number written on the masking tape and a separate log will be kept to ensure that correct anesthetic was used after the random assignment.

6.1.5 Dosing and Administration

The initial dose administered for both groups will be one cartridge of anesthetic (1.8 mL for Bupivacaine, 1.7 mL for Lidocaine). The dose rationale will be followed up as described in section 2.2.2 *Dose Rationale and 6.1.7 Starting Dose and Dose Escalation Schedule*.

6.1.6 Route of Administration

IANB is the route of administration.

6.1.7 Starting Dose and Dose Escalation Schedule

The initial dose administered for groups will be one cartridge (1.8 mL for Bupivacaine, 1.7 mL for Lidocaine).

If adequate anesthesia is not achieved within 15 minutes determined by the treating dentist by;

1. Asking the subject for reporting of lip numbness

CONFIDENTIAL

2. Testing and comparing with the contralateral side of the lip with a blunt instrument such as mirror handle, a second injection of the same dosage of the same drug will be provided.

If the IANB fails to provide adequate lip numbness after the second injection after a wait time of a further 15 minutes (total wait time 30 minutes), the subject will discontinue with the study agent/control agent, will be excluded from the study and the treating dentist will be unblinded and routine protocol will be followed; Lidocaine 2% with 1:100,000 epinephrine will be administered either with an IANB, infiltration or intraosseous anesthesia as decided by the treating dentist.

[figure not shown]
Whether the adequate lip numbness is gained either after the 1st or 2nd IANB, another 10 minutes will be waited to achieve pulpal anesthesia;

1. Cold Test - As per standard of care, Endo-Ice (Coltene, USA) will be administered to subjects to determine the success of pulpal anesthesia. This is a routine step in endodontic treatment. A cotton pellet is sprayed with the refrigerant spray and applied the tooth. A painful response will indicate inadequate pulpal anesthesia.

Subjects in each group will also receive a buccal infiltration and IL injection with Lidocaine which is highly recommended for symptomatic teeth. The Cold Test will be repeated to determine anesthesia. The algorithmic chart for anesthetic administration in Fig. 1 will be followed as the guideline. Additional supplemental injections will be administered as portrayed in the chart with Lidocaine HCl 2% 1:100,00 in both groups if needed, until pulpal anesthesia is obtained to initiate treatment or to continue with the treatment, without jeopardizing the maximum dose limit for the subject.

Subjects who need supplemental injections more than 2 times will be excluded from the study

Figure 1: Algorithm to Follow Adequate Soft Tissue and Pulpal Anesthesia

CONFIDENTIAL

6.1.8 Duration of Therapy

The duration of the therapy begins with the administration of the IANB. The duration of the treatment is approximately 1-2 hours. The subject will then be followed remotely for 5 days.

The duration of study participation will be from the 1st treatment visit, until the participant returns for their second routine endodontic treatment visit. At this second visit, compensation will be given and data collection will be finalized, if necessary. This is in an effort to coincide the research visit with the routine and needed dental visit. This visit will be scheduled by the treating dentist and can be anywhere up to several weeks after the first treatment visit. There will be no time limit for this research visit. If the patient will return to the school for an appointment in another department/clinic, they can inform the research team and efforts will be made to meet the patient then if the 5 days post-treatment data collection is complete.

6.1.9 Tracking of Dose

The dose of anesthesia used both for IANB and for supplemental anesthesia will be recorded by a study investigator.

6.2 Study Agent Accountability Procedures

One carton containing 5 blisters of 10X1.8 mL of Bupivacaine, in total containing 50 cartridges and one cartoon containing 5 blisters of 10X1.7 mL Lidocaine in total containing 50 cartridges will be obtained initially from the Endodontic supply desk. Those cartons will be stored in a locked cabinet on the 7th floor, which will be only accessible by 2 post graduate (PG) students who are only delegated for study agent accountability procedures.

The two PG students who are only delegated for the study agent accountability procedures and blinding and randomization procedures will remove all drug cartridges from the blisters, wrap them with opaque tape and write a cartridge number assigned by Biostatistics prior to recruitment and place them in a container which will have the name of the drug. The same procedure will be done for the Lidocaine group. These two containers will be stored in a locked cabinet on 7th floor along with the blisters. This pre-wrapping will take place in order to not to waste time during the time of treatment.

A study product log will be created and maintained by these 2 PG students. The study product log will be signed and dated each time one of the two PG student removes a pair of cartridges. New cartons will be obtained from the supply desk when necessary and documented in the log. Unused product will be returned at the end of the treatment, if the cartridge is untampered. The two PG students will be responsible for maintaining this log and will reconcile the log each week assigned, to document drug consumed, and remaining.

6.3 Study Procedural Intervention Description

IANB, which is the route of administration for obtaining anesthesia for mandibular molars, will be the interventional procedure with the study and the control agent in both groups. It will be followed by routine pulpectomy/endodontic debridement treatment.

6.3.1 Administration of Procedural Intervention

The study product in both treatment groups will be administered by the treating post PG student Endodontic student in the endodontic clinic. This treating dentist may be a study investigator. In this case, the investigator will be blinded to the randomization. Another study investigator will be present to provide assistance for the research visit. All study related interventions and standard of care treatments which become part of the research will be overseen by NYS Dental Licensed faculty who are listed as Co-Investigators.

6.3.2 Procedures for Training of Clinicians on Procedural Intervention

PG endodontic students who have been trained for at least 6 months in the Endodontic program at NYU Dentistry will administer both the IANB and the pulpectomy/endodontic debridement. PG endodontic students are actively treating patients and have had all relevant didactic lectures before they start to treat

CONFIDENTIAL

This material is the property of the NYU School of Medicine and Langone Medical Center. Do not disclose or use except as authorized in writing by the study sponsor

patients with symptomatic teeth for providing a standardized endodontic care. Before the beginning of the trial, they will be reviewed about the steps to follow for anesthetic administration and treatment in order to standardize the treatment they provide.

6.3.3 Assessment of Clinician and/or Participant Compliance with Study Procedural Intervention

By direct observation, clinician and participant compliance will be assessed by the study PI routinely.

7 Study Procedures and Schedule

7.1 Study Procedures/Evaluations

7.1.1 Study Specific Procedures

1. Screening, Consent and Preoperative Data Collection:

The potential participant's standard of care clinical and radiographic examination findings, diagnosis and treatment plan approved by the faculty who are NYS Dental Licensed Co-Investigators, will be prescreened by one of the study investigators after the standard of care clinical and radiographic examinations performed by the treating dentist to determine whether the patient is eligible in terms of diagnosis and treatment plan approved by the faculty by reviewing the gathered findings. This will be done in an effort to not to increase the wait time period for patients.

After prescreening, potential participant will be asked by their dental provider who are PG students who work under the supervision of Co-Investigators, if they are interested in discussing participation in a research study regarding postoperative pain with a research investigator. Interested subjects will be introduced to the study by the PI or Co-I; [name]. If they agree to participate, they will be consented by the PI or Co-I; [name].

Interested potential subjects will be screened for eligibility by one of the study investigators and will be enrolled if they meet all the eligibility criteria.

The following questionnaires will be completed to collect demographic information, psychological state information and trait characteristics, preoperative pain, and baseline oral quality of life information:

- Subject Demographic and Medical/Dental/Pain History Form
- Pain Catastrophizing Scale (PCS)
- Oral Health Impact Profile (OHIP14)

2. Randomization and Blinding:

Subjects will be assigned a de-identified subject number upon enrollment in the study. Subjects will be randomly assigned to one of two study groups in a 1:1 ratio just before receiving anesthesia; 0.5% Bupivacaine with 1:200,000 epinephrine OR 2% Lidocaine with 1:100,000 epinephrine.

The randomization schema will be provided by the unblinded statistician and will be implemented using the REDCaP randomization module. Two PG students ([name], [name]) who are part of the study team, but are only delegated for the study agent accountability procedures and blinding and randomization procedures will wrap all of the drug cartridges of Bupivacaine with opaque tape and write on the vials a cartridge number assigned by the statistician prior to recruitment and place them in a container which will have the name of the drug. The same procedure will be done for the Lidocaine group. These two containers will be stored in a locked cabinet on 7th floor. At the time when a subject is recruited by the treating resident and is found eligible and signs a consent, one of the 2 PG students will be notified and will log onto REDCaP and retrieve the randomization for the subject within the appropriate stratum (Lidocaine/Bupivacaine), pick up a pair of 2 pre-wrapped cartridges in accordance with the randomization scheme, write on the wrapped cartridges the assigned subject number in the consult room on the 7th floor, privately in order to prevent unintentional unblinding, log electronically the subject number with the corresponding numbers of the pair of cartridges assigned to subject, and hand it to the treating resident.

CONFIDENTIAL

3. IANB Administration, Testing Pulpal Anesthesia:

The initial dose administered for groups will be one cartridge (1.8 mL for Bupivacaine, 1.7 mL for Lidocaine).

If adequate anesthesia is not achieved within 15 minutes determined by the treating dentist by;

1. Asking the subject for reporting of lip numbness
2. Testing and comparing with the contralateral side of the lip with a blunt instrument such as mirror handle, a second injection of the same dosage of the same drug will be provided.

If the IANB fails to provide adequate lip numbness after the second injection after a wait time of a further 15 minutes (total wait time 30 minutes), the subject will discontinue with the study agent/control agent, the treating dentist will be unblinded and routine protocol will be followed; Lidocaine 2% with 1:100,000 epinephrine will be administered either with an IANB, infiltration or intraosseous anesthesia as decided by the treating dentist. This patient will be excluded from the study.

After the adequate lip numbness is gained, another 10 minutes will be waited to achieve pulpal anesthesia; Cold Test – As per standard of care, Endo-Ice (Coltene, USA) will be administered to subjects to determine the success of pulpal This is a routine step in endodontic treatment. A cotton pellet is sprayed with the refrigerant spray and applied the tooth. A painful response will indicate inadequate pulpal anesthesia.

Subjects in each group will also receive a buccal infiltration and IL injection with Lidocaine which is highly recommended for symptomatic teeth. The Cold Test will be repeated to determine anesthesia. The algorithmic chart for anesthetic administration in the supplementary form *Pulpectomy/Endodontic Debridement Method* will be followed as the guideline. Additional supplemental injections will be administered as portrayed in the chart with Lidocaine HCl 2% 1:100,00 in both groups if needed, until pulpal anesthesia is obtained to initiate treatment, without jeopardizing the maximum dose limit for the subject.

Subjects who need supplemental injections more than 2 times will be excluded the study.

4. Intra- and Immediate Post-operative Data Collection:

- Pre-operative data obtained after clinical and radiographic examination which are performed as standard of care, before the treatment procedure, such as cold test response, percussion hypersensitivity, pulpal and periapical diagnosis will be collected by a study investigator by the end of the treatment, together with the intraoperative and immediate postoperative data.
- Intraoperative data such as number of cartridges used, time for adequate anesthesia, additional supplementary anesthesia will be collected.
- Intraoperative pain will be evaluated on a NRS by asking the subject directly after treatment.

5. Remote Data Collection:

Subjects will receive surveys remotely either by e-mail through REDCap, which will ask about their pain intensity reported on an NRS, analgesic medication use and numbness. REDCap surveys will be sent at 6, 12, 24, 48, 72, 96 and 120 hours after treatment. On day 1 and 5, subjects will be assessed by OHIP14.

If subjects do not have access to the Internet, a study team member will call them. Paper questionnaires will also be an option if no other methods are convenient for subjects. If they prefer to fill in the questions and questionnaire on paper, they will be asked to bring them to their second appointment.

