Endpoints	
Primary Study Endpoint
 
 • Oral health related quality of life OHIP-14 score changes from preoperative to postoperatively on day 1 and day 5. 
Secondary Study Endpoints
 
 • Postoperative pain intensity during 5 days • Number and type of pain medication use • Duration of LA in hours (numbness) after receiving pulpectomy/endodontic debridement 
Exploratory Endpoints
 
 • Cold test results (+/-) • Number of supplemental injections • Duration until adequate lip numbness is obtained (in minutes) • Duration until negative cold response is obtained (in minutes)
Study Duration	The estimated duration of this study is 1 year
Participant Duration	4 weeks ± 10 days (until the second appointment with the subject)
Duration of IP administration	
The duration of administration of either Bupivacaine or Lidocaine as an inferior alveolar nerve block (IANB) lasts up to two minutes.
 
The duration of anesthesia following administration is up to 7 hours for Bupivacaine and up to 4 hours for Lidocaine.

Population	Patients presenting to the NYU Dentistry Department of Endodontics for endodontic care for a symptomatic mandibular molar tooth, aged between 18-85 years, any gender, all demographic and ethnic groups and ASA I or II.
Study Sites	NYU College of Dentistry Department of Endodontics
Number of Participants	We plan to enroll 50 subjects in each group; approximately 100 participants will be enrolled. 20% dropout rate is expected, with an expected 40 subjects in each group.
Description of Study Agent/Procedure	Bupivacaine is an FDA approved anesthetic drug, commercially available (0.5% Bupivacaine with 1:200,000 epinephrine) routinely administered intraorally by IANB.
Reference Therapy	Lidocaine is an FDA approved anesthetic drug, commercially available (2% Lidocaine with 1:100,000 epinephrine) routinely administered intraorally by IANB.
Key Procedures	Preoperative data collection, administration of an IANB (Bupivacaine or Lidocaine), followed by standard of care 1 st visit endodontic procedure; pulpectomy/endodontic debridement. Postoperative data collection during 5 days after treatment.

CONFIDENTIAL

[figure not shown]
This material is the property of the NYU School of Medicine and Langone Medical Center. Do not disclose or use except as authorized in writing by the study sponsor

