2.1 Background Information and Relevant Literature

Patients have been reported to suffer from moderate to severe pain after endodontic treatment for up to seven days, and of those the first 2 days pain is commonly the most severe (1). It has been shown that preoperative pain is the one of the major predictors of postoperative pain (2) which suggests that postoperative pain management becomes even more crucial for patients who report to the clinic with ongoing preoperative pain.

It has also been found that preoperative percussion hypersensitivity (mechanical allodynia) of an offending tooth has been shown to be one of the major predictors of severe postoperative pain after emergency treatments (3), 92% of the patients who attended emergency endodontic clinic had a painful response to percussion on the tooth in questions (4). Percussion hypersensitivity has been associated with central sensitization (5, 6) therefore, postoperative pain management can be an especially important in patients with a diagnosis of symptomatic apical periodontitis and painful percussion responses.

Postoperative management strategies have been suggested that usually include non-steroid anti-inflammatory drugs (NSAID) and/or acetaminophen (7), opioids (8), and corticosteroids (9). Alternatively, administration of LLA, bupivacaine, which can last up to 7-12 hours, has been suggested as a strategy to manage postoperative pain (10-12). A meta-analysis on efficacy and safety of bupivacaine versus lidocaine showed statistically significant better postoperative pain control with bupivacaine after dental treatment and no difference in safety when compared with lidocaine (10). It has been hypothesized that with the use of LLA, inhibits peripheral barrage from primary afferent neurons after the treatment and thereby significantly inhibit sensitization of second order neurons in the pain pathway that then will lead to reduction or elimination of central sensitization resulting in reduction of postoperative pain, not only during the LLA period but also after the resolution of the anesthesia (13).

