4.1.2 Secondary Study Endpoints

- Postoperative pain intensity during 5 days
- Number and type of pain medication use
- Duration of LA in hours (numbness) after receiving pulpectomy/endodontic debridement

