7.2.3 Remote Data Collection

Subjects will be asked to rate their pain intensity on an NRS, report analgesic use and numbness:

- 6 hours after treatment
- 12 hours after treatment
- 24 hours after treatment
- 48 hours after treatment
- 72 hours after treatment
- 96 hours after treatment
- 120 hours after treatment

- Day 1 – OHIP14 questionnaire

- Day 5 – OHIP14 questionnaire

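### Numbness duration in hours is a secondary endpoint, but numbness is first asked about 6 hours after treatment and nothing in the plan says the time when sensation returns is recorded

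*Combined protocol and SAP*

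**What the plan says.** Section 4.1.2 lists as the third secondary endpoint "Duration of LA in hours (numbness) after receiving pulpectomy/endodontic debridement", and section 3.2 gives it its own objective.

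After the patient leaves the chair, the data come from remote questionnaires. Section 7.2.3 states "Subjects will be asked to rate their pain intensity on an NRS, report analgesic use and numbness", and section 7.1.1 gives the times: "REDCap surveys will be sent at 6, 12, 24, 48, 72, 96 and 120 hours after treatment". There is no contact between the end of treatment and 6 hours.

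Section 6.1.8 fixes the start of the procedure and its length: "The duration of the therapy begins with the administration of the IANB. The duration of the treatment is approximately 1-2 hours".

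The documents give more than one figure for how long numbness lasts:
- Protocol Summary: "The duration of anesthesia following administration is up to 7 hours for Bupivacaine and up to 4 hours for Lidocaine".
- Section 2.1: "administration of LLA, bupivacaine, which can last up to 7-12 hours".
- Section 2.2.1: two to three times as long as lidocaine, with 7 hours given for many patients and not as a ceiling.
- Sections 13.3.1 and 13.3.2: patients are told 3-7 hours of soft-tissue anesthesia.

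Section 10.2.4 analyses numbness, together with pain and medication use, by longitudinal mixed models over the five postoperative days.

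The intraoperative data in section 7.1.1 cover the onset of anesthesia, not its end. Section 10.1.2 mentions abnormally prolonged anesthesia as something a patient would report, but only as an adverse event. No section says that the time of return to normal sensation is noted by anyone. The follow-up questionnaires are listed in section 18, but their item wording is not in the documents.

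**The concern.** An endpoint in hours needs a start time and an end time for each patient. The schedule makes its first observation late compared with the durations the protocol quotes, and the text provides no other record of the end. If the survey asks whether the patient is numb now, the answers are statuses on a coarse grid. If it asks how long numbness lasted, the answer reconstructs a moment that the patient was not asked to note.

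Longer soft-tissue numbness is the drawback that sections 2.1 and 2.3 set against better pain control, and this endpoint measures it directly. With poor capture, a real difference between the arms could be blurred, or could rest on recall of differing length in the two arms. The primary OHIP-14 comparison is not affected.

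**Working it through.** The documents state no computed figure on this point, so the check is timeline arithmetic.

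**Inputs**
- Survey times after treatment: 6, 12, 24, 48, 72, 96 and 120 h (sections 7.1.1 and 7.2.3).
- Treatment length T, counted from the block: about 1-2 h (section 6.1.8).
- Duration D from administration: lidocaine up to 4 h, bupivacaine up to 7 h (Protocol Summary); bupivacaine up to 12 h as the top of the section 2.1 range.
- Section 2.2.1 multiple applied to 4 h: 2 × 4 = 8 h to 3 × 4 = 12 h.

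I read the survey clock as starting at the end of the procedure.

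**Step 1. Surveys on the injection clock** (survey time + T)
- First: 6 + 1 = 7 h to 6 + 2 = 8 h.
- Second: 12 + 1 = 13 h to 12 + 2 = 14 h.

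**Step 2. Latest end of numbness on the treatment clock** (D − T)

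| Arm and figure | End after treatment | Interval containing the end | Surveys while numb |
|---|---|---|---|
| Lidocaine, 4 h | 2-3 h | 0-6 h | 0 of 7 |
| Bupivacaine, 7 h | 5-6 h | 0-6 h | 0 of 7 |
| Bupivacaine, 8 h | 6-7 h | 0-6 h if T = 2; 6-12 h if T = 1 | 0 or 1 of 7 |
| Bupivacaine, 12 h | 10-11 h | 6-12 h | 1 of 7 |

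The lidocaine row is the same on every figure given: no survey falls during numbness. For bupivacaine, at most one survey does.

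**Step 3. How much the 6-hour survey could show.** The documents give no distribution of durations, so I assume a uniform one on [a, b] as an illustration only. The share still numb at the first survey is (b − t)/(b − a), limited to 0-1, with t = 7 or 8 h after injection.
- 3-7 h: (7 − 7)/4 = 0% for T = 1, and 0% for T = 2.
- 4-12 h: (12 − 7)/8 = 62.5% to (12 − 8)/8 = 50%.
- 7-12 h: (12 − 7)/5 = 100% to (12 − 8)/5 = 80%.

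At the 12-hour survey (13-14 h after injection) the share is 0% in all three cases. What the schedule shows about the bupivacaine arm therefore runs from nothing to a clear yes/no contrast, depending on which of the protocol's figures is right. In no case does it give hours.

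**Step 4. Recall gap if the item asks for a completed duration**
- Lidocaine: end by 2-3 h, asked at 6 h, so the gap is at least 6 − 3 = 3 h to 6 − 2 = 4 h.
- Bupivacaine on the 7 h figure: end by 5-6 h, so the gap is at least 0-1 h.

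The minimum gap differs between the arms.

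**Step 5. Time zero.** Counting from the end of treatment takes T, or 1-2 h, off each patient's value. The gap between the two upper figures is unchanged: 7 − 4 = 3 h from injection, and 5 − 2 = 3 h or 6 − 3 = 3 h from the end of treatment for the same T.

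**Step 6. Planned model.** One duration per patient leaves no repeated measure to model. If repeated status is modelled instead, Step 2 shows that at most one of seven occasions can be positive, and only in one arm.

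**The case against.** A reader might infer that the schedule cannot observe this endpoint at all. The documents do not support that. A survey sent after numbness has ended can still ask how long it lasted, and an endpoint defined in hours fits such an item. The wording sits in an attachment that is not available, so its content cannot be assumed either way. What stands is that the protocol text specifies no end time and that any recalled time refers to a moment the patient was not told to note.

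A reader might also infer that numbness will be over in both arms before anyone is asked. That holds for lidocaine. For bupivacaine it holds on the 7-hour figure only; sections 2.1 and 2.2.1 allow longer, and then the 6-hour survey could separate the arms, though only as yes or no. If the survey clock in fact starts at injection, the first survey comes at 6 h and some bupivacaine patients could be numb even on the 7-hour figure.

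Nor is counting from the end of treatment an error. It is the protocol's own endpoint definition, it describes the burden after leaving the chair, and Step 5 shows that it leaves the contrast intact. The 3 hours is itself a difference between two upper figures; the protocol does not state it as an expected effect.

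Finally, this is one of three secondary endpoints, and sections 2.1 and 2.3 also expect OHIP-14 to reflect the functional cost of numbness. That limits the weight of the point but does not supply the missing end time.

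**Conclusion.** The point holds as a measurement gap in a secondary endpoint. The first question about numbness falls about 7-8 h after injection, by which time every lidocaine patient, and on the 7-hour figure every bupivacaine patient, should have recovered. On the longer figures some bupivacaine patients would still be numb.

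Status answers alone would yield two coarse intervals: 0-6 h for all lidocaine patients, and 0-6 h or 6-12 h for bupivacaine patients. Recall answers would rest on an unrecorded moment. The five-day longitudinal model fits neither a single duration nor a status that can be positive at one survey at most.

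This rests on three assumptions: the survey clock starts at the end of a procedure of about 1-2 h, the quoted durations run from administration, and the unseen questionnaire does not already collect a noted clock time. If it does, what remains is to say so in the protocol, name the time zero and replace the model.

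**What to change.** 1. Record on the intraoperative form the clock time of the block (the last one if two are given) and of the end of treatment.
2. At discharge, ask patients to write down the clock time when the lip feels fully normal.
3. Collect that time in the 6-hour survey, and again at 12 and 24 hours from those still numb. Keep a current-status question at each of these surveys.
4. State one time zero, either injection or end of treatment, and report the other as a sensitivity analysis.
5. In section 10.2.4, replace the mixed model for this endpoint with a comparison of one duration per patient: a two-sample test, or a time-to-event method that treats patients without a noted time as interval-censored between the last survey reporting numbness (or time zero) and the first reporting normal sensation.
6. Reconcile the duration figures in the Protocol Summary and sections 2.1, 2.2.1, 13.3.1 and 13.3.2.

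The cost is two recorded times, one reworded survey item, one line in the discharge instructions and a short edit to the analysis section. No visit and no change in sample size is needed. Section 2.4.1 already has patients advised to be careful with chewing until sensation is normal, so they have reason to notice the moment. The downside is one extra thing for the patient to note.
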